Cardiovascular Inflammation Reduction Trial (CIRT) Inflammation Imaging
[name]
NCT02576067
Document Date: March 7, 2019

	Protocol Title:	Cardiovascular Inflammation Reduction Trial (CIRT) Inflammation Imaging Study
	Principal Investigator Name/Contact Info:	[name]/[contact]
	Primary Contact Name/Contact Info:	[name]: [REDACTED]; [name]: ext. [REDACTED]
	Date Revised:	March 7, 2019
	Study Number:	GCO# 14-1382; IF2430508; HS# 14-00185

MSSM Protocol Template HRP-503a

Instructions:

1. Prepare a document with the following sections. Note that, depending on the nature of your research, certain sections below may not be applicable. Indicate N/A as appropriate, explaining where possible.
2. For any items described in the sponsor's protocol, grant application or other source documents submitted with the application, you may reference the title and page numbers of these documents rather than cutting and pasting into this document. **Do NOT refer to any derived documents, such as the Sample Consent document, or other internal documents required with the submission.**
3. If you reference page numbers, attach those pages to this protocol.
4. When you write a protocol, keep an electronic copy. You will need to modify this copy when making changes.

Brief Summary of Research (250-400 words):

Vascular inflammation, a central feature of atherosclerosis, participates in the initiation, perpetuation and instability of plaques. Multiple clinical trials of cholesterol lowering therapy with statins have demonstrated that reductions in atherosclerotic cardiovascular disease (CVD) events are associated with reductions in both LDL cholesterol (LDL-C) and the systemic inflammatory mediator C-reactive protein (CRP). The Cardiovascular Inflammation Reduction Trial (CIRT) investigates if an anti-inflammatory agent commonly used in rheumatoid arthritis (low dose methotrexate (LDM)) can reduce CV morbidity and mortality among patients with a prior myocardial infarction or angiographically demonstrated multivessel coronary artery disease (GCO#13-1467).

In this ancillary CIRT imaging study, we propose to use this well validated approach by non-invasive serial FDG-PET/CT imaging in a subset of patients enrolled in the main CIRT trial to directly visualize vascular inflammation. Once the subjects are enrolled in the main CIRT trial, baseline imaging will be done and follow up imaging will be done approximately 8 months after the baseline imaging. To clarify, we anticipate on having the randomization visit to follow closely after the baseline imaging visit, which means that subjects will be coming approximately 8 months after the randomization visit in the main CIRT Trial.

¹⁸FDG-PET imaging data will be acquired, analyzed centrally and results incorporated into the main CIRT database. We hypothesize that LDM treatment will result in a significant decrease in plaque inflammation as measured by 18-FDG-PET/CT after 8 months as compared to placebo.

1) Objectives:

Research Question:

To determine the impact of anti-inflammatory treatment with LDM on arterial

	Protocol Title:	Cardiovascular Inflammation Reduction Trial (CIRT) Inflammation Imaging Study
	Principal Investigator Name/Contact Info:	[name]/[contact]
	Primary Contact Name/Contact Info:	[name]: [contact]; [name]: [name]
	Date Revised:	March 7, 2019
	Study Number:	GCO# 14-1382; IF2430508; HS# 14-00185

inflammation, as assessed by FDG-PET/CT imaging in patients with stable coronary artery disease who are at increased risk. We will determine the effect of LDM on the change from baseline in the target (plaque) to background (blood) ratio (TBR) based on 18-FDG uptake measured with PET/CT after 8 months of weekly dosing with LDM (primary endpoint).

To evaluate changes in imaging endpoints in relation to changes in systemic inflammatory biomarkers (especially high sensitivity C-reactive protein (hs-CRP)).

2) Background

The NHLBI funded ([name] 5U01HL101422) Cardiovascular Inflammation Reduction Trial (CIRT) provides a unique opportunity to investigate whether a commonly used anti-inflammatory agent used in rheumatoid arthritis (low dose methotrexate (LDM)) can reduce CVD morbidity and mortality among patients with stable coronary artery disease. CIRT, is a randomized, double-blind, placebo-controlled, multi-center trial among 7,000 men and women with prior myocardial infarction or angiographically demonstrated multivessel coronary artery disease. Eligible participants will be randomly allocated over a three to four year period to usual care plus placebo or usual care plus LDM (average dose of 15-20 mg po/weekly. CIRT proposes that the reduction in CVD events with methotrexate derives from its effect on vascular inflammation, thus it is crucial to incorporate a measure of vascular inflammation imaging for confirmation of the primary mechanism of action underlying CIRT. As such, the direct evaluation of arterial inflammation would enhance the scientific value of the CIRT trial.

The inclusion of the proposed vascular inflammation imaging substudy has widespread implications that will allow this imaging modality to serve as a surrogate measure of disease, and thereby provide an opportunity for stratification in individuals at risk for CVD and evaluation of other interventions with presumed anti-inflammatory effects.

(Please see Protocol NIH CIRT imaging for more details -pages 104).

Current protocol for the Main CIRT trial as well as CIRT imaging sub study are provided as an Appendix

3) Setting of the Human Research

The total study duration is 38-40 weeks which includes a pre-randomization phase (up to 8 weeks), and a double-blind treatment phase (approximately 32 weeks). There will be four imaging centers (Mount Sinai Medical Center, New York, NY, University Health Network, Ontario, Canada, Massachusetts General Hospital, Boston, MA, and University of California San Francisco (UCSF), San Francisco, CA), which will perform all the imaging for the surrounding referring centers. There will be recruiting centers in each region (New York, Toronto, and Boston) for 17 centers in total. For the NY region, the 7 recruiting centers where the subjects will be identified and recruited will be Montefiore Medical Center ([name]), Winthrop University Hospital ([name] - PI), NewYork-Presbyterian Queens ([name]), Weill Cornell Medical Center (Dr.

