	Study Number:	GCO# 14-1382; IF2430508; HS# 14-00185

d) Study Timelines

Timelines		Year 1				Year 2				Year 3				Year 4			
Task	Month	0-3	3-6	6-9	9-12	12-15	15-18	18-21	21-24	24-27	27-30	30-33	33-36	36-39	39-42	42-45	45-48
Study Startup		█															
Patient recruitment		█	█	█	█	█	█	█	█	█							
Baseline Imaging			█	█	█	█	█	█	█	█							
Follow up Imaging						█	█	█	█	█	█	█	█	█	█		
Image Analysis										█	█	█	█	█	█		
Statistical Analysis															█	█	█
Manuscripts Publication																	█

(Please see Protocol NIH CIRT imaging for more details -pages 111, 116).

e) Study Endpoints

Imaging endpoints (SA 1): The endpoints (relative change (LDM vs. placebo, through 8 months)) in arterial inflammation based on PET imaging are as follows:

Primary endpoint used to evaluate vascular inflammation is most diseased segment (MDS) of the index vessel. The MDS is defined as the 1.5 cm segment within the carotid artery (right or left carotid) that demonstrates the highest PET/CT activity, and is calculated as a mean of maximum TBR values derived from 3 contiguous axial segments. The index vessel in turn is defined as the vessel (either aorta, right, or left carotid) with the greatest mean TBR at baseline.

Secondary endpoints will include: i) The mean of max TBR within the carotid arteries as an average of the slices from the left and right carotid) or ii) as combined (carotid and aorta); iii) the mean of the maximum TBR of all of the slices that compose the index vessel, and iv) Standardized uptake value (SUV) of each vessel analyzed (left carotid, right carotid and ascending aorta)

	Protocol Title:	Cardiovascular Inflammation Reduction Trial (CIRT) Inflammation Imaging Study
	Principal Investigator Name/Contact Info:	[name]/[contact]
	Primary Contact Name/Contact Info:	[name]: [contact]; [name]: [name]
	Date Revised:	March 7, 2019
	Study Number:	GCO# 14-1382; IF2430508; HS# 14-00185

[figure not shown]

Figure 3: Sample images of aorta obtained using 18-FDG PET/CT and corresponding imaging endpoints determined

(Please see Protocol NIH CIRT imaging for more details-page 114).

Current protocol for the Main CIRT trial as well as CIRT imaging sub study are provided as an Appendix.

f) Procedures Involved in the Human Research

Table 1: Workflow for each imaging visit	
Time (minutes)	Action
Before imaging visit	Subject is consented for CIRT imaging trial at main CIRT clinical site

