-360	Subjects begins fast (only oral hydration permitted)
0	Subject arrives at imaging facility
5	Subject changes into hospital clothing(gown) and prepared for study
10	IV inserted for injection of FDG and for drawing blood
12	10 ml of blood is drawn for biomarker assessments
13	Blood glucose measurements for determining eligibility for FDG injection
15	10milli Curie of FDG injected into subject
105	Subject rests in a relaxed position to allow FDG circulation
120	Aorta PET/CT scans acquired
135	Carotid PET/CT scans acquired
140	Subject prepped for leaving (miscellaneous, instructions for future visits)
150	Imaging visit completed, subject leaves imaging center

(Please see Protocol NIH CIRT imaging for more details -pages 112 - 113 (Table 1), 116)

Timing of imaging visits as part of the CIRT imaging substudy: The first (baseline) imaging will take place prior to the open label run in of Low Dose Methotrexate in the CIRT main trial (between V1 and V2 of main CIRT). The second (follow up) imaging visit will take place 8 months after randomization into the main CIRT trial (close to V6 of main trial).

	Protocol Title:	Cardiovascular Inflammation Reduction Trial (CIRT) Inflammation Imaging Study
	Principal Investigator Name/Contact Info:	[name]/[contact]
	Primary Contact Name/Contact Info:	[name]: [contact]; [name]: [name]
	Date Revised:	March 7, 2019
	Study Number:	GCO# 14-1382; IF2430508; HS# 14-00185

Due to early closure of the main CIRT Trial, subjects who have not reached the 8 months final imaging timepoint will be asked to go to their Imaging Center by the end of May 2018 and/or till all final imaging visits are completed, as advised by NHLBI. Subjects who have been on the Imaging substudy for 5 months or less after their baseline scan will need to be seen within this new time period.

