The DSMB was constituted by the NHLBI and will be composed of members from the following areas: 1) physicians with specific expertise in the clinical management of cardiovascular disease 2) a biostatistician with specific expertise in the design, analysis, and safety monitoring of multi-center clinical trials 3) a medical ethicist, and 4) a physician with specific expertise in rheumatologic disease. The DSMB will oversee the main CIRT trial as well as the CIRT Imaging Study and the physician with expertise on rheumatologic disease will be from the Brigham and Women's Hospital site which will also provide the overall programmatic and statistical support for the CIRT Imaging Study. [name] who is the PI of the CIRT Imaging Study and [name] who is the co-investigator of the CIRT Imaging Study will take part in the semiannual review.

The Committee members will collect and review the safety data every 6 months and be responsible for review of:

- a) study recruitment goals and tracking of enrollment;
- b) presentation of spreadsheets for data analysis;
- c) adverse and reportable events as defined by the investigators;

As of 4/2/18, enrollment has ended due to early termination of the main CIRT Trial. There will no longer be any DSMB meetings.

(Please see Protocol NIH CIRT – imaging for more details: pages 120-122).

j) Withdrawal of Subjects

	Protocol Title:	Cardiovascular Inflammation Reduction Trial (CIRT) Inflammation Imaging Study
	Principal Investigator Name/Contact Info:	[name]/[contact]
	Primary Contact Name/Contact Info	[name]: [contact]; [name]: [name]
	Date Revised:	March 7, 2019
	Study Number:	GCO# 14-1382; IF2430508; HS# 14-00185

Participation in this imaging study is voluntary. The subjects can withdraw at any time by informing the PI and/or the study coordinators. Although the subjects can withdraw from the imaging study, they can still continue to participate in the CIRT main trial.

6) Risks to Subjects

Risks associated with 18-FDG-PET/CT:

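### The primary endpoint has no defined segment when the aorta is the index vessel, its scale is stated two ways, and no model or baseline covariate is named; ANCOVA on baseline TBR would add modest precision

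*Combined protocol and SAP*

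**What the plan says.** Section 1, Objectives, states the primary effect: "We will determine the effect of LDM on the change from baseline in the target (plaque) to background (blood) ratio (TBR". Section e, Study Endpoints, uses another expression: "The endpoints (relative change (LDM vs. placebo, through 8 months)) in arterial inflammation based on PET imaging are as follows". It does not say whether that is a percent change within subject or a contrast between arms.

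The same section makes the MDS of the index vessel the primary measure and then defines its two parts differently:

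- "The MDS is defined as the 1.5 cm segment within the carotid artery (right or left carotid) that demonstrates the highest PET/CT activity"
- "The index vessel in turn is defined as the vessel (either aorta, right, or left carotid) with the greatest mean TBR at baseline"

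On timing, section f says: "The first (baseline) imaging will take place prior to the open label run in of Low Dose Methotrexate in the CIRT main trial". On design, section 2 says: "CIRT, is a randomized, double-blind, placebo-controlled, multi-center trial among 7,000 men and women".

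No section gives an analysis model, a covariate or a scale. Item 5 of the Data and Safety Monitoring Plan says that the main features of the statistical plan are outlined in the protocol. The template's instructions also allow short cuts: "you may reference the title and page numbers of these documents rather than cutting and pasting into this document". Study Endpoints refers to page 114 of the NIH imaging protocol, which is not part of this document.

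**The concern.** Three things needed to fix the primary analysis are open: the region measured, the scale of the effect, and the model.

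The region matters most. If a subject's highest mean TBR is in the aorta, the index vessel is the aorta, but the MDS is defined only in a carotid. The primary endpoint then points to nothing, and so does any baseline covariate built on it. The text also ties the choice of vessel to the baseline scan without saying whether the segment is fixed from that scan or chosen again at follow-up.

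As to the model, if change is compared between arms without adjustment, the estimate moves with chance baseline imbalance and is less precise than ANCOVA. This counts more if the analysed number fell short of the planned 170, which is possible: "As of 4/2/18, enrollment has ended due to early termination of the main CIRT Trial". Naming the model and scale in advance also removes a later choice among change, percent change and adjusted analysis.

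**Working it through.** **Inputs from the document.** Planned total 170 (section c); randomised, placebo-controlled design (section 2); baseline scan before the run-in (section f). The document gives no alpha, power, effect size, SD or correlation, so 170 cannot be reproduced.

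**Assumed inputs.** 1:1 allocation (85 per arm), two-sided alpha 0.05, test-retest correlation r from 0.5 to 0.9, equal SDs at the two scans unless stated.

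**1. The region.** The eligible vessels are the aorta and the two carotids; the MDS is allowed only in the carotids. With three exchangeable vessels the aorta is the index vessel in 1/3 = 33% of subjects. In simulation the share is 16-19% if the aortic mean is 0.5 SD lower and 51-56% if it is 0.5 SD higher. These shifts are illustrative. The contradiction itself needs no assumption.

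**2. Bias.** In 4,000 simulated trials of 170 at each of three correlations, with the highest of three vessels at baseline taken as index vessel and a true effect of -0.30, mean estimates were -0.303, -0.297 and -0.298 for change and -0.302, -0.297 and -0.298 for ANCOVA. Both are unbiased.

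**3. Precision without selection on baseline.** Var(change) is proportional to 2(1 - r) and Var(ANCOVA) to 1 - r². The ratio is (1 + r)/2: 0.75 at r = 0.5, 0.85 at 0.7, 0.95 at 0.9. This fits the secondary endpoints that involve no baseline selection (i, ii and iv).

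**4. Precision for the MDS.** Taking the vessel and segment with the highest baseline value narrows the baseline spread, so step 3 overstates the gain. The simulation used a true component plus independent error at each scan, two or three eligible vessels with true cross-vessel correlation 0.5, and 4, 6 or 10 segments per vessel. A share of 0.2 or 0.5 of the true variance lay within vessels, with 200,000 subjects per setting.

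| Segment at follow-up | Var(ANCOVA)/Var(change) | Variance lower by | Extra subjects to match (1/ratio - 1) |
|---|---|---|---|
| Fixed from baseline | 0.900 to 0.992 | 10% to 1% | 11% to 1% |
| Re-selected | 0.782 to 0.963 | 22% to 4% | 28% to 4% |

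**5. Power.** Where change has 80% power, ANCOVA power is Φ(2.802/√ratio - 1.96):

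- Fixed: 2.802/√0.900 = 2.954, power 84.0%; 2.802/√0.992 = 2.813, power 80.3%. Gain 4.0 to 0.3 points.
- Re-selected: 2.802/√0.782 = 3.169, power 88.7%; 2.802/√0.963 = 2.855, power 81.5%. Gain 8.7 to 1.5 points.

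Simulated trials with two carotids, within-vessel share 0.5, 6 segments and r = 0.5 agree to within simulation error: 78.7% against 82.3% (fixed) and 80.1% against 89.1% (re-selected).

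**6. Cost of the covariate.** Estimating the slope inflates variance by about 1 + 1/(N - 4). At N = 170 this is 1 + 1/166 = 1.006; at N = 80 it is 1 + 1/76 = 1.013. With a ratio of 0.992, the net ratio is 0.992 × 1.006 = 0.998 at 170 and 0.992 × 1.013 = 1.005 at 80. The gain is then nil or slightly negative.

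**7. Unequal SDs.** With k = follow-up SD/baseline SD and no selection, the ratio is k²(1 - r²)/(1 + k² - 2rk). For k = 0.8 and r = 0.5: 0.48/0.84 = 0.57. For k = 1.25 and r = 0.7 it is 0.98. The ranges in step 4 therefore hold only for equal SDs.

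**The case against.** The strongest reply is that the text shows no wrong model. The sentence in the Objectives defines an endpoint, and regressing change on arm and baseline gives the same treatment coefficient as regressing follow-up on them. The wording is thus fully compatible with ANCOVA. The document says a statistical plan is outlined, is allowed to cite pages instead of repeating them, and sends endpoint detail to the NIH imaging protocol. All of this stands. A reader might infer that an unadjusted comparison is planned, or that there is no statistical plan; the text supports neither.

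A reader might also suspect that choosing the hottest vessel at baseline biases the arm difference through regression to the mean. It does not: the choice precedes randomisation and affects both arms alike (step 2).

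It is also fair to say that the size is assumed throughout, that the larger gains require re-selection of the segment, which the text does not state, and that percent change was not simulated. Power differences of a few tenths of a point between simulated settings are noise. Lastly, the document is dated March 2019, after enrolment ended, so it may have been too late to change the primary model blind. None of this resolves the carotid and aorta conflict, which is visible on the page, or the two expressions of scale.

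**Conclusion.** The point holds as a request to complete the specification, and as a plain contradiction in the endpoint definition. A subject whose index vessel is the aorta has no defined primary segment, whatever the model. The scale must also be settled.

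On the model, the conclusion is conditional: if change is compared unadjusted, the comparison is valid but somewhat less precise than it need be. The gain for the primary endpoint is modest, roughly 1-10% of variance with a fixed segment and 4-22% with a re-selected one. The textbook reduction of 25% at r = 0.5 should not be carried over to an endpoint selected on its baseline value. These figures rest on assumed correlations, equal SDs, 1:1 allocation and a normal model, which can be read as log TBR. Confidence is medium, because the NIH pages may already name the model.

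**What to change.** 1. Reconcile Study Endpoints so that the MDS and the index vessel refer to one region, and state that the same region is measured at baseline and follow-up.
2. Choose one scale in place of change and relative change; use log TBR if a relative effect is meant.
3. Unless the NIH pages already specify it, in which case a cross-reference is enough, make the primary analysis an ANCOVA of follow-up TBR on arm and baseline TBR of that region, on that scale. Record this before unblinding. Use the same model for the secondary TBR and SUV endpoints, each with its own baseline.
4. If unblinded analysis has begun, report the ANCOVA as a labelled additional analysis.

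The cost is a dated amendment or SAP entry and one degree of freedom, with no new data. This does not deal with follow-up scans taken before 8 months because of the early closure, which need their own provision.

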The recruiting centers will be responsible for identifying suitable subjects for the study, recruiting the subjects into the study, informed consent, blood work and arranging for transportation of the subjects to the imaging centers as part of the CIRT imaging substudy. This is a sub study of the parent NHLBI funded CIRT trial ([name] 5U01HL101422). Only subjects that are part of the main CIRT study and have consented to being approached for ancillary studies will be approached for recruitment into this CIRT imaging substudy. In the main CIRT trial, patients are recruited from 300 to 400 clinical sites (average of 20 randomized participants per site) in the US and Canada, all of whom have demonstrated experience in the identification, randomization, and long-term follow-up of patients with cardiovascular disease. In CIRT, as of August 14th, 2015, 4,559 subjects have answered the question regarding being contacted for ancillary study participation in the ICF. Taking out those who have withdrawn, 2,662 subjects have answered the question. Of these 2,662 subjects, 2,192 have consented to be contacted and 470 have not consented to be contacted.

	Protocol Title:	Cardiovascular Inflammation Reduction Trial (CIRT) Inflammation Imaging Study
	Principal Investigator Name/Contact Info:	[name]/[contact]
	Primary Contact Name/Contact Info	[name]: [contact]; [name]: [name]
	Date Revised:	March 7, 2019
	Study Number:	GCO# 14-1382; IF2430508; HS# 14-00185

The total subjects to be recruited for the CIRT Imaging substudy will be 170 (56 to 57 subjects are planned to be imaged in each of the three Imaging Centers). Only subjects recruited to the main trial will be recruited to the imaging substudy. The imaging study team will support main CIRT recruitment by using study flyers and postcard distributed at the Cardiac units, inpatients and outpatients clinics inside the Mount Sinai Health System, within the New York metropolitan area.

(Please see Protocol NIH CIRT imaging for more details -pages 111-112, 121).

Subjects will be consented for the imaging substudy by the clinical PI at the main CIRT trial centers during their initial study visit for the main CIRT trial. Subjects will also sign a consent form for the imaging sub study at the imaging center unless the PI obtaining consent is affiliated with the institution where the imaging center is located; in which case, the subjects will only sign one consent form for the imaging substudy. More details are provided in the “consent process” section.

b) Inclusion and Exclusion Criteria

The FDG-PET/CT imaging study will be performed as a substudy of CIRT, the inclusion/exclusion criteria for this imaging sub-study will include all of those of the main trial.

(Please see protocol NIH CIRT Imaging for more details -pages 117-118)

Inclusion Criteria include the following:

- a. Age \geq 18 years at screening
- b. Documented MI in the past or past evidence of multivessel coronary artery disease by angiography must have completed any planned coronary revascularization procedures associated with the qualifying event, and must be clinically stable for at least 60 d before screening; the qualifying prior MI must be documented either by hospital records or by evidence on current electrocardiogram of Q waves in 2 contiguous leads and/or an imaging test demonstrating wall motion abnormality or scar; the qualifying documentation of multivessel coronary disease must include angiographic evidence of atherosclerosis in at least 2 major epicardial vessels defined either as the presence of a stent, a coronary bypass graft, or an angiographic lesion of 60% or greater. Left main coronary artery disease that has been revascularized with a stent or bypass graft will qualify as multivessel disease, as will the presence of a 50% or greater isolated left main stenosis.
- c. History of type 2 diabetes or metabolic syndrome at the time of study enrollment
- d. Willing to participate as evidence by signing the study informed consent

Exclusion Criteria include the following:

1. Prior history of chronic infectious disease, including tuberculosis, severe fungal disease, or known HIV positive
2. Chronic hepatitis B or C infection

	Protocol Title:	Cardiovascular Inflammation Reduction Trial (CIRT) Inflammation Imaging Study
	Principal Investigator Name/Contact Info:	[name]/[contact]
	Primary Contact Name/Contact Info:	[name]: [contact]; [name]: [name]
	Date Revised:	March 7, 2019
	Study Number:	GCO# 14-1382; IF2430508; HS# 14-00185

3. Interstitial pneumonitis, bronchiectasis, or pulmonary fibrosis. Chest x-ray evidence in the past 12 months of interstitial pneumonitis, bronchiectasis, or pulmonary fibrosis.
4. Prior history of non basal cell malignancy or myeloproliferative or lymphoproliferative disease within the past 5 years
5. White blood cell count $<3,500/\text{mm}^3$, hematocrit $<32\%$, or platelet count $<75,000/\text{mm}^3$
6. Liver transaminase levels (AST/ALT) greater than the upper limit of normal or albumin less than the lower limit of normal
7. Creatinine clearance (CrCl) <40 mL/min as estimated by the Cockcroft-Gault equation
8. History of alcohol abuse or unwillingness to limit alcohol consumption to <4 drinks per week
9. Women of child bearing potential, even if currently using contraception, and women intending to breastfeed
10. Men who plan to father children during the study period or who are unwilling to use contraception
11. Requirement for use of drugs that alter folate metabolism (trimethoprim/sulfamethoxazol) or reduce tubular excretion (probenecid) or known allergies to antibiotics making avoidance of trimethoprim impossible
12. Current indication for methotrexate therapy
13. Chronic use of oral steroid therapy or other immunosuppressive or biologic response modifiers
14. Known chronic pericardial effusion, pleural effusion, or ascites
15. New York Heart Association class IV congestive heart failure
16. Life expectancy of <3 years

The study population for the ancillary study will be the same as the main trial with the following additional exclusion criteria

- a. Subjects with a history of multiple imaging studies associated with radiation exposure
- b. If subject is Type 2 diabetic, hemoglobin A1c greater than 8% as determined by patient medical record review in the one year prior to the date of consent to this study.
- c. BMI greater than $37 \text{ kg}/\text{m}^2$ or weight greater than 350 pounds

c) Number of Subjects

The total subjects to be recruited for the CIRT Imaging will be 170 (56 to 57 in each of the three Imaging Centers).

(Please see Protocol NIH CIRT imaging for more details -pages 111-112).

	Protocol Title:	Cardiovascular Inflammation Reduction Trial (CIRT) Inflammation Imaging Study
	Principal Investigator Name/Contact Info:	[name]/[contact]
	Primary Contact Name/Contact Info:	[name]: [contact]; [name]: [name]
	Date Revised:	March 7, 2019
	Study Number:	GCO# 14-1382; IF2430508; HS# 14-00185

d) Study Timelines

Timelines		Year 1				Year 2				Year 3				Year 4			
Task	Month	0-3	3-6	6-9	9-12	12-15	15-18	18-21	21-24	24-27	27-30	30-33	33-36	36-39	39-42	42-45	45-48
Study Startup		█															
Patient recruitment		█	█	█	█	█	█	█	█	█							
Baseline Imaging			█	█	█	█	█	█	█	█							
Follow up Imaging						█	█	█	█	█	█	█	█	█	█		
Image Analysis										█	█	█	█	█	█		
Statistical Analysis															█	█	█
Manuscripts Publication																	█

(Please see Protocol NIH CIRT imaging for more details -pages 111, 116).

e) Study Endpoints

Imaging endpoints (SA 1): The endpoints (relative change (LDM vs. placebo, through 8 months)) in arterial inflammation based on PET imaging are as follows:

Primary endpoint used to evaluate vascular inflammation is most diseased segment (MDS) of the index vessel. The MDS is defined as the 1.5 cm segment within the carotid artery (right or left carotid) that demonstrates the highest PET/CT activity, and is calculated as a mean of maximum TBR values derived from 3 contiguous axial segments. The index vessel in turn is defined as the vessel (either aorta, right, or left carotid) with the greatest mean TBR at baseline.

Secondary endpoints will include: i) The mean of max TBR within the carotid arteries as an average of the slices from the left and right carotid) or ii) as combined (carotid and aorta); iii) the mean of the maximum TBR of all of the slices that compose the index vessel, and iv) Standardized uptake value (SUV) of each vessel analyzed (left carotid, right carotid and ascending aorta)

	Protocol Title:	Cardiovascular Inflammation Reduction Trial (CIRT) Inflammation Imaging Study
	Principal Investigator Name/Contact Info:	[name]/[contact]
	Primary Contact Name/Contact Info:	[name]: [contact]; [name]: [name]
	Date Revised:	March 7, 2019
	Study Number:	GCO# 14-1382; IF2430508; HS# 14-00185

[figure not shown]

Figure 3: Sample images of aorta obtained using 18-FDG PET/CT and corresponding imaging endpoints determined

(Please see Protocol NIH CIRT imaging for more details-page 114).

Current protocol for the Main CIRT trial as well as CIRT imaging sub study are provided as an Appendix.

f) Procedures Involved in the Human Research

Table 1: Workflow for each imaging visit	
Time (minutes)	Action
Before imaging visit	Subject is consented for CIRT imaging trial at main CIRT clinical site
-360	Subjects begins fast (only oral hydration permitted)
0	Subject arrives at imaging facility
5	Subject changes into hospital clothing(gown) and prepared for study
10	IV inserted for injection of FDG and for drawing blood
12	10 ml of blood is drawn for biomarker assessments
13	Blood glucose measurements for determining eligibility for FDG injection
15	10milli Curie of FDG injected into subject
105	Subject rests in a relaxed position to allow FDG circulation
120	Aorta PET/CT scans acquired
135	Carotid PET/CT scans acquired
140	Subject prepped for leaving (miscellaneous, instructions for future visits)
150	Imaging visit completed, subject leaves imaging center

(Please see Protocol NIH CIRT imaging for more details -pages 112 - 113 (Table 1), 116)

Timing of imaging visits as part of the CIRT imaging substudy: The first (baseline) imaging will take place prior to the open label run in of Low Dose Methotrexate in the CIRT main trial (between V1 and V2 of main CIRT). The second (follow up) imaging visit will take place 8 months after randomization into the main CIRT trial (close to V6 of main trial).

	Protocol Title:	Cardiovascular Inflammation Reduction Trial (CIRT) Inflammation Imaging Study
	Principal Investigator Name/Contact Info:	[name]/[contact]
	Primary Contact Name/Contact Info:	[name]: [contact]; [name]: [name]
	Date Revised:	March 7, 2019
	Study Number:	GCO# 14-1382; IF2430508; HS# 14-00185

Due to early closure of the main CIRT Trial, subjects who have not reached the 8 months final imaging timepoint will be asked to go to their Imaging Center by the end of May 2018 and/or till all final imaging visits are completed, as advised by NHLBI. Subjects who have been on the Imaging substudy for 5 months or less after their baseline scan will need to be seen within this new time period.

Subject will be asked to verify with a physician insulin regiment for fasting and dieting needed prior to each imaging visit and provide study team with physician's recommendations whether to continue with our imaging study. On the day of the visit, the subject will be able to proceed with the imaging only when fasting glucose is equal or less than 170 mg/dL and equal or greater than 80 mg/dL. This will be verified at our site prior to the scan by finger stick or i.v. If the fasting blood glucose is less than 80 mg/dL each subject will be instructed to eat a snack or we will provide sugar cubes. Once fasting blood glucose is above 80 mg/dL, we will proceed with the imaging.

g) Specimen Banking

Ancillary Study Data Collection. This ancillary proposal will additionally collect the following data from each study subject participating in the imaging ancillary study

- 1) PET/CT Imaging data in the form of DICOM images.
- 2) Blood draw for evaluation of inflammatory biomarkers. These samples will also be stored in a coded fashion. The blood will only be stored for the purpose of the trial.
- 3) Blood draw for evaluation of pre scan glucose. This is an instant test and the data are not stored. This information is used only to determine if the subject is eligible for FDG injection at the time of imaging or if the imaging test needs to be postponed. Patients with a fasting glucose of >170 mg/dl will need to be rescheduled for an on-trial FDG-PET scan at a later date (p. 112 of other protocol)
- 4) Only the PIs of the imaging sub study and the main CIRT trial and their authorized representatives will have access to the code that links the imaging and blood data back to each individual subject. The linking files will be stored securely on a hard disk in Co-investigator's office.

(Please see Protocol NIH CIRT imaging for more details-page 119).

h) Data Management and Confidentiality

Image identifiers (blinded data) will be removed by the imaging site investigators and prepared for transfer to the Mount Sinai PET/CT Core Laboratory using either secure FTP or by mailing CDs with DICOM data. All Images will be coded and be identified only by a study ID number. All coded image data will also be stored at the central laboratory for imaging (Mount Sinai) on encrypted hard disks specific to this trial (CIRT image data repository). Only study personnel authorized to evaluate images, the imaging data manager and the PI will have access to imaging data. All imaging data and meta-analysis files are also stored on the same encrypted hard disk (image data repository). The image data repository has access controls and an audit trail feature built in using Mac Hg version control. This system is 21 CFR Part 11 compliant.

	Protocol Title:	Cardiovascular Inflammation Reduction Trial (CIRT) Inflammation Imaging Study
	Principal Investigator Name/Contact Info:	[name]/[contact]
	Primary Contact Name/Contact Info:	[name]: [contact]; [name]: [name]
	Date Revised:	March 7, 2019
	Study Number:	GCO# 14-1382; IF2430508; HS# 14-00185

(Please see Protocol NIH CIRT imaging for more details -page 113).

i) Provisions to Monitor the Data to Ensure the Safety of subjects

Data for the substudy will be linked to the parent database by subject identification number only. The Mount Sinai imaging data coordinating center has programs, policies and procedures in use at all times to ensure the security and confidentiality of the data. Direct identifiable variables such as name, address, DOB, MRN, SSN, that can link the data to a person's identity will not be sent to us from the imaging sites. Only coded data is received at the core laboratory and is identifiable only by the subject ID). Research data files will be stored using this ID as the unique identifier. The linking code file which contains the linking information between the unique identifier and the direct identifiable variables will be stored in a different location than the de-identified and identifiable information and is available only to the PI and select individuals.

Part I: Elements of a Data and Safety Monitoring Plan

MSSM Principal Monitor:

Last Name: [name]
 First Name: [name]
 Academic Title: Professor
 Department: CVI
 Mailing Address: [REDACTED]
 Phone: [REDACTED]
 Email: [contact]

MSSM Additional Monitor:

Last Name: [name]
 First Name: [name]
 Academic Title: Associate Professor
 Department: Radiology
 Mailing Address: [REDACTED].
 Phone: [REDACTED] 1
 Email: [contact]

2. Justify your choice of principal monitor in terms of the assessed risk to the research subject's health and wellbeing. In high risk studies when the principal monitor is independent of the study staff, indicate the individual's credentials, relationship to the PI, and the rationale for selection.

	Protocol Title:	Cardiovascular Inflammation Reduction Trial (CIRT) Inflammation Imaging Study
	Principal Investigator Name/Contact Info:	[name]/[contact]
	Primary Contact Name/Contact Info:	[name]: [contact]; [name]: [name]
	Date Revised:	March 7, 2019
	Study Number:	GCO# 14-1382; IF2430508; HS# 14-00185

The investigators and research team are experienced in conducting clinical trials, trained (having met the IRB’s educational requirements) and knowledgeable about the protocol, and are therefore qualified to review safety updates, monitor subjects for adverse events and assess their health and well-being during the trial. The additional monitor is also an expert in imaging and will be responsible for the safety of the subjects during their imaging visits. The co-investigators and the research team are responsible for the safety and welfare of the subjects and for conducting the trial as outlined in the protocol.

3. List the specific items that will be monitored for safety (e.g., adverse events, subject compliance with the protocol, drop outs, etc.).

Additional items that will be monitored during their imaging visit will be a chance of swelling, pain, bruising, infection or redness during blood draw; subject compliance which will also be monitored by the subject's main site and subjects will also be monitored for reactions during the injection of the 18-FDG radiotracer although there are no known side effects with the use of the agent.

*4. Indicate the frequency at which **ACCUMULATED** safety and data information (items listed in number 3 above and interim analysis of efficacy outcomes) will be reviewed by the monitor(s) or the Data Monitoring Committee (DMC). Although this information must be reviewed at least annually, the higher the study risks, the more frequently reviews must be scheduled.*

